### **6.8 Premature Termination or Suspension of Study**

This study may be temporarily suspended or prematurely terminated if there is sufficient reasonable cause. Written notification, documenting the reason for study suspension or termination, will be provided by the suspending or terminating party to the investigator, funding agencies, and regulatory authorities. If the study is prematurely terminated or suspended, the PI will promptly inform the IRB and will provide the reason(s) for the termination or suspension.

Circumstances that may warrant termination or suspension include, but are not limited to:

- Determination of unexpected, significant, or unacceptable risk to participants
- Demonstration of efficacy that would warrant stopping
- Insufficient compliance to protocol requirements
- Data that are not sufficiently complete and/or evaluable
- Determination of futility

Study may resume once concerns about safety, protocol compliance, data quality are addressed and satisfy the sponsor, IRB and/or FDA.

### **6.9 Acquisition**

During the index visit, BUP (as a BUP-NX formulation) will be acquired from the Bellevue Hospital ED and NYULH Pharmacy medication dispensing system, where it is on formulary and approved for this indication. Upon completion of the third research visit or upon development of objective signs of opioid withdrawal (determined via COWS), participants will be provided with a prescription for sublingual BUP-NX, which they can acquire free of charge from the outpatient hospital pharmacy, located adjacent to the BHC ED.

#### **6.9.1 Formulation, Appearance, Packaging, and Labeling**

All BUP ordered as part of clinical care in the EMR and supplied through the Bellevue Hospital Clinical Pharmacy and NYULH Clinical Pharmacy. Currently on Bellevue Hospital formulary is the generic buprenorphine/naloxone (8mg/2mg) tablet and Subutex brand BUP monoproduct (the latter would be for use in patients/participants with a naloxone allergy only). The manufacturer will depend on what is currently on the hospital formulary and may change. Should this occur, participants will receive the equivalent medication dose. For example, if the formulary changes from BUP-NX (8mg/2mg) tablet to buprenorphine/naloxone (8mg/2mg) film, the participant will receive buprenorphine/naloxone (8mg/2mg) film sublingually (same bioavailability/dose).

Participants will also receive a prescription for BUP to pick up at their preferred outpatient pharmacy either after the third research visit, or when they demonstrate objective signs of withdrawal.

There will be no storage or administration of medication by the research pharmacy.

#### **6.9.2 Product Storage and Stability**

Study Number: s19-01700

Version: 7.0

Version Date: 08/01/2022

As above, medication will be ordered as part of clinical care and supplied through the Bellevue Hospital clinical pharmacy and NYULH clinical pharmacy. There will be no research medication stored/supplied by the study.

### **6.9.3 Preparation**

The study agent does not require additional preparation.

### **6.9.4 Dosing and Administration**

All participants will receive a total dose of BUP 32mg sublingually in divided doses during the index ED visit. After the participant has received a total of 8mg (as a single dose or in divided doses), BUP SL 24mg will be administered (i.e., 8mg + 24mg, or 4mg + 4mg +24mg). A dose of up to BUP 8mg SL may be administered by the clinical provider prior to enrollment of the patient-participant (i.e., given clinically, not as a research procedure).

After pre-medication assessments are complete and the participant is confirmed to have a COWS of  $\geq 8$ , the participant will be given BUP SL to reach a dose of 8mg. Starting 30 minutes after BUP administration, the participant will be reassessed for withdrawal severity and any adverse events. As long as there are no unexpected significant adverse events, an additional BUP 24mg SL will be administered. Then, participants will be monitored and reassessed every 30 minutes for a period of at least 90 minutes after receiving the last dose of BUP.

Participants will return on days 1, 2, and 3 for research visits. At those visits, participants will be assessed for opioid withdrawal using the COWS scale. On the first day that the participant has objective signs of opioid withdrawal (via COWS), the [name], who is a licensed physician with an X-waiver for BUP prescription, or another study clinician (with the appropriate license and X-waiver) will electronically send a prescription the participant's preferred outpatient pharmacy for a daily dose of BUP 16mg (BUP or BUP/NX 8/2mg: two SL) to start immediately. Participants will be prescribed a quantity sufficient to ensure medication coverage until the date of their appointment for ongoing treatment with a (non-study) OUD treatment provider. Participants who do not exhibit opioid withdrawal at any of the visits on days 1-3, will be given a prescription upon completion of the day 3 visit with instructions to self-administer upon emergence of symptoms of opioid withdrawal or craving.

All participants will receive a referral to be seen by a provider experienced in treating OUD. Thereafter, continued treatment and specific daily dosage of BUP-NX will be a joint decision between the study participant and the healthcare provider.

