### 1.1.1 Schedule of Research Events

	Research Visits				
	Index	Day 1	Day 2	Day 3	Day 30
Eligibility and Enrollment					
Potential participants identified by staff referral and/or research staff screening	x				
Approval of clinical provider (confirmation that medically and psychiatrically stable and appropriate for study participation)	x				
Written Informed Consent and Medical Release	x				
Eligibility Assessments and Checklist (DSM-5 OUD, Medical exam, COWS)*	x				
Assessments					
Demographics (PhenX)	x				
Drug Use Inventory and other Substance Use Measures (PhenX, TLFB)	x	x	x	x	x
Urine and/or Saliva Toxicology (Standard panel, BUP, FEN)	x				
Withdrawal and Craving Measures (COWS, SOWS, scales)*	x	x	x	x	x
Quality of life and treatment (PROMIS-GLOBAL- 10, TEA)	x	x	x	x	x
Overdose and risk assessments	x	x	x	x	x
Qualitative Assessments/Participant Satisfaction	x	x	x	x	x
Non-Study Medical and Other Services (NMS)	x	x	x	x	x
Adverse Events	x	x	x	x	x
Administrative Actions and Review					
Appointment scheduling for research visits and follow up care	x	x	x	x	
Participant compensation (value)	80	40	40	40	40
Round Trip Metrocard	x	x	x	x	
Healthcare Utilization Review		x	x	x	

\*Multiple assessments conducted before BUP dose 1, after BUP dose 1, and after BUP dose 2

Study Number: s19-01700

Version: 7.0

Version Date: 08/01/2022

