#### 3.1 Primary Objective

1. To estimate the proportion and confidence intervals of participants who have “*successful rapid induction*” (as further defined below) amongst enrolled participants who receive a loading dose of BUP SL 32mg during the ED index visit. Successful rapid induction is defined only be the outcome of the participant’s visit, and not by any following research visits.

Hypothesis: All participants who receive a loading dose of BUP SL 32mg will have successful rapid induction. Successful rapid induction is defined as receiving a total of 32 mg of buprenorphine SL at the index research visit without experiencing a clinically significant serious and/or severe adverse event related to the intervention. Loss to follow up in subsequent research visits will not impact this outcome measure.

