## 5 Study Endpoints

### 5.1.1 Primary Study Endpoints

#### 1. To estimate the proportion having “*successful rapid induction*”

*Successful Rapid Induction*, the primary study endpoint, is defined as completing rapid induction with a loading dose of BUP SL 32mg without experiencing a clinically significant serious and/or severe adverse event (AE) related to the intervention – specifically, the receipt of a dose of BUP SL greater than 8mg during the Index ED visit. We will determine the proportion of participants who have successful rapid induction during the ED index visit amongst all study participants.

- *Clinically significant adverse events* (AEs) include the following: over-sedation (defined as requiring invasive or non-invasive ventilator support, having a Richmond Agitation-Sedation Scale (RASS) of  $\leq -3$ , and/or clinician determination), hemodynamic instability (e.g., persistent hypotension not attributed to other causes), development of severe precipitated withdrawal

Study Number: s19-01700

Version: 7.0

Version Date: 08/01/2022

(clinician determination), or experiencing other unexpected, SAEs, related to receipt of the second dose of BUP SL (for a total of BUP SL 32mg) as defined in *Section 8.1*. This measure will be assessed at the end of the ED index visit.

- Precipitated withdrawal: Clinicians will assess whether an event is considered precipitated withdrawal. This clinical determination will be based on the severity of the withdrawal signs and symptoms, the rapidity of the onset of withdrawal symptoms, and clinical factors (e.g. timing since last use of an opioid agonist(s), type(s) of opioid agonist, duration of action of opioid agonist(s) used, and route of administration). Scores will be based on objective components, eliminating nausea which can be a side effect of BUP administration. Patients who experience precipitated withdrawal will be treated with ancillary medications.

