#### **6.7 Participant Withdrawal or Termination**

##### **6.7.1 Reasons for Withdrawal or Termination**

Participants are free to withdraw from participation in the study at any time upon request. An investigator may terminate participation in the study if:

- After the first 8 mg dose of BUP is administered, a study participant experiences any clinical AE (e.g., allergic reaction) that would preclude safe administration of the subsequent BUP 24mg dose during the index visit. The initial BUP 8mg is a standard dose used in the ED; it is only the subsequent BUP 24mg (for a total dose of BUP 32mg) that is being evaluated in this study.
- Thus, if a participant develops a reaction to the initial 8mg dose, the reaction would be attributed to the standard dose of BUP and not the larger dose of being tested.
- The participant meets an exclusion criterion (either newly developed or not previously

Study Number: s19-01700

Version: 7.0

Version Date: 08/01/2022

recognized) that precludes further study participation.

- The participant becomes a prisoner.

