## **7.4 Study Schedule**

### **7.4.1 Screening**

### **7.4.2 Enrollment/Baseline**

#### **Index ED Visit (Day 0, 4 – 8 hours)**

- Perform baseline assessments:
  - Obtain demographic information, medical/psychiatric history, medication history, substance use history.
  - Obtain informed consent of potential participant verified by signature on written informed consent for screening form.
  - Perform medical examinations needed to determine eligibility based on inclusion/exclusion criteria.
  - Review history and verify inclusion/exclusion criteria.
  - Collect urine or saliva samples for toxicology testing, collect urine for a pregnancy test (in females of childbearing potential, if not performed clinically).
  - Assess and quantitate opioid and other substance use, withdrawal, craving, motivation for treatment, health status questionnaire, health services utilization).
- Participants receive total 32mg BUP in divided doses. After the participant has received a total of 8mg, participants will be observed for 30 minutes to ensure that there are no adverse reactions to BUP-NX. If the participant has a qualifying adverse event after the first dose (e.g., allergic reaction or other clinically significant AEs as described in Section 5.1.1), the second dose will not be given and the participant will be withdrawn from the study without receiving subsequent doses. Otherwise, the second dose of 24 mg will be administered.
- Participants will be assessed using opioid withdrawal scales (COWS, SOWS, VAS) prior to BUP administration and every 30 minutes afterward for at least 90 minutes after last dose.
- Participants will be discharged with 4 scheduled appointments, 3 research visits (days 1, 2, 3), an appointment for follow up with a BUP provider for ongoing OUD treatment, and a research follow-up phone call on Day 30, which marks the end of the study for the participant.
- In light of the health safety risks associated with the COVID-19 pandemic, interviews may be conducted remotely, rather than in-person, using an approved, secure audio or audio-video connection (e.g., telephone, Cisco Webex) from a setting offering adequate privacy. Participants will be advised that they may disconnect their video feed.

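### Pre-enrolment dosing and an unsettled denominator leave the primary success proportion enriched, by an unstated amount, for people who tolerated the first 8 mg

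*Combined protocol and SAP*

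**What the plan says.** **Two routes to the first 8 mg.** Section 6.9.4 allows "A dose of up to BUP 8mg SL may be administered by the clinical provider prior to enrollment of the patient-participant", as clinical care and not as a study procedure. Anyone who has not yet had the full 8 mg is brought up to it in the study, and the 24 mg dose follows.

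**Reaction before enrolment.** The schedule in 1.1.1 requires the clinical provider's approval ("confirmation that medically and psychiatrically stable and appropriate for study participation"). Section 2.1.6 excludes people with a previous adverse reaction. Section 6.2 excludes known allergy and anyone whom the study clinician or provider judges unsafe to take part. Section 8.3 records adverse events only from informed consent.

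**Reaction to a study-given first dose.** Section 7.4.2 says that "the second dose will not be given and the participant will be withdrawn from the study without receiving subsequent doses". Section 6.7.1 adds that "the reaction would be attributed to the standard dose of BUP and not the larger dose of being tested", and 6.7.2 continues enrolment after withdrawals until 35 is reached.

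**Primary endpoint.** Section 5.1.1 says "We will determine the proportion of participants who have successful rapid induction during the ED index visit amongst all study participants" and describes success through "the receipt of a dose of BUP SL greater than 8mg during the Index ED visit". Section 3.1 estimates the proportion "amongst enrolled participants who receive a loading dose of BUP SL 32mg during the ED index visit".

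Section 10.1 plans descriptive analysis of this proportion. It sets no denominator and does not separate the two routes.

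**The concern.** Whether a person can fail at the first step depends on who gave the first dose and on which section defines the denominator. A reactor to a clinical pre-dose will usually be absent from the data. A reactor to a study dose is either a failure (5.1.1) or is removed (3.1, or withdrawal with replacement under 6.7). In both cases the reported proportion describes people who tolerated 8 mg better than the average patient offered the strategy. Under 5.1.1 the degree also depends on how many participants happened to be pre-dosed.

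This matters because section 3.1 hypothesises that all participants will succeed, and sections 2.1.3 and 3 say that the results will be used to plan large trials. A later trial that gives every dose after enrolment would meet first-step failures that this estimate partly or wholly leaves out.

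**Working it through.** The sample size of 35 rests on feasibility (10.1), so the plan has no statistical figure to reproduce. The check is a simple selection model.

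**Inputs**
- n = 35, from sections 6.6 and 10.1.
- r = proportion whose reaction to the first 8 mg stops further dosing. Not given; assumed 3-10%.
- f = share of participants given the full first 8 mg before enrolment. Not given; assumed 25-75%.
- q = failure rate after the 24 mg dose. Not given; taken as 0, with 3% as a check.
- All pre-enrolment reactors are assumed to be kept out. This is a simplification that gives the largest effect.

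**Formulas, q = 0**
- Success among everyone given a first dose: 1 − r.
- Section 5.1.1 (all participants, reactors fail): only the share 1 − f can fail at the first step, so success is 1 − (1 − f)r and the excess is f × r.
- Section 3.1, or withdraw and replace: every counted participant has tolerated 8 mg, so success is 1 and the excess is r, whatever f is.

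**Results: excess in percentage points**

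| r | 5.1.1, f = 25% | 5.1.1, f = 50% | 5.1.1, f = 75% | 3.1 or replaced |
|---|---|---|---|---|
| 3% | 0.75 | 1.5 | 2.25 | 3 |
| 5% | 1.25 | 2.5 | 3.75 | 5 |
| 10% | 2.5 | 5.0 | 7.5 | 10 |

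In the central case, 1 − 0.5 × 0.05 = 97.5% against 95.0%. That is 0.025 × 35 = 0.9 participants. The upper corner is 0.075 × 35 = 2.6 participants.

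**Sensitivity**
- If f is the share among all first-dosed patients instead of among participants, 5.1.1 gives (1 − r)/(1 − f r) = 0.95/0.975 = 97.4%, almost the same.
- With q = 3%, r = 5% and that second definition of f at 50%, the excess is 2.4 points under 5.1.1. On the other reading it is r(1 − q) = 0.05 × 0.97 = 4.85 points.
- The only event figure in the documents is the chart review in 2.1.3, with no events in 94 patients. Its exact 95% upper limit is 1 − 0.025^(1/94) = 3.8%. Using that as r with f = 50% gives 1.9 points. Those patients had already received 24-32 mg, so the figure may understate r.

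**Scale**
- The exact 95% interval at 35/35 runs from 0.025^(1/35) = 90.0% to 100%.
- At r = 5% the chance of observing 35/35 under 5.1.1 is 0.95^35 = 17% if all are dosed in the study, and about 0.975^35 = 41% if half are pre-dosed.

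**The case against.** **The target may be the 24 mg step only.** Section 6.7.1 says that only the second dose is under evaluation, and 5.1.1 links at least one of its disqualifying event types to that dose. For that question, conditioning on tolerance of 8 mg is legitimate. This stands, but the condition must then be stated, and 5.1.1 should not fail first-dose reactors. The objective in section 3 is the whole 32 mg strategy, and the plan does not choose between the two.

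**The routes may not differ.** A reader might infer that study-dosed reactors definitely count as failures while pre-dosed ones vanish. The documents do not support that firmly. It follows from 5.1.1, but under 3.1, or under 6.7 read as withdraw and replace, both kinds of reactor leave the proportion. The enrichment is then larger and no longer depends on pre-dosing.

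**Pre-enrolment reactors are not always lost.** A reader might infer that they never enter. Section 2.1.4 says that precipitated withdrawal does not necessarily bar further dosing and leaves the decision to the study clinician. Section 4.2 logs reasons for people approached but not enrolled, so some reactors may be visible. That log has a gap: under 6.4.1 the team asks the treating provider's permission before meeting the patient, so a reactor whom the provider holds back may never be approached.

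**Selection can run the other way.** COWS of at least 8 is required before study dosing (6.1, 6.9.4), and this may screen out pre-dosed patients who responded well. A patient pre-dosed with only part of the 8 mg can still react in the study. The direction at the first step is clear; the net difference between routes is not.

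**The effect is small beside the sampling error.** At low reaction rates this is true, given an interval of 90.0-100% at 35/35. But that interval does not reflect selection, and section 10.1 does not name dosing route among its example cross-tabulations.

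**Conclusion.** The point holds in a limited form. Most reactors to a clinical pre-dose will be missing from the data, and the plan does not settle whether reactors to a study dose count. On either denominator the proportion overstates success among all patients given a first dose.

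Under 5.1.1 the excess is about 2.5 points at r = 5% and f = 50%, and about 0.8 to 7.5 points over the ranges tried. Under 3.1 or replacement it is the full reaction rate when no failures occur after the second dose. All of these sizes rest on assumed r and f and on complete exclusion of pre-enrolment reactors; the documents cannot confirm any of them. The 7.5-point figure needs both upper assumptions together.

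A reader might also infer that the result will vary by site or by provider habit. The documents give no pre-dosing rates by site or provider, so that is only a possibility.

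**What to change.** 1. **One denominator.** Reconcile sections 3.1, 5.1.1, 6.7.1 and 6.7.2, and repeat the result in 10.1: who is counted, and whether a participant who reacts to a study-given first dose is a non-success or outside the estimate. Keep every enrolled and dosed participant in the report, even if replaced. Splitting by route without this step would not help, because under 3.1 the group first dosed after enrolment is just as enriched.
2. **Report by route.** Give the primary proportion with exact intervals overall and by buprenorphine received before enrolment: none, part, or all of the first 8 mg.
3. **Planning figure.** For a trial that doses from the start, use the group first dosed after enrolment, with first-dose reactors kept in the denominator. If the target is only the 24 mg step, say that the result is conditional on tolerating the first 8 mg.
4. **Screening log.** For all screened or referred patients, not only those approached, record any pre-enrolment dose and add a reaction to the clinical pre-dose as a non-enrolment reason. Report the count.

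The cost is a few sentences, some table rows and one reason code. Subgroup intervals will be wide: at 17/17 the exact lower limit is 0.025^(1/17) = 80.5%. Dosing does not change.
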